**Version: 13 / October 2018**

## **INTRODUCTION**

Considerable research has sought to overcome the limitations of available anticoagulant and antithrombotic agents. This includes efforts to develop agents that target specific factors of the coagulation process, which in turn may improve efficacy and increase the therapeutic index. Warfarin acts through inhibition of multiple areas on the coagulation cascade and the direct oral anticoagulants (DOACs) like (Dabigatran/Rivaroxaban/Apixaban/Edoxaban). Factor Xa is a primary target since this factor plays a pivotal role in the coagulation cascade at the junction of the intrinsic and extrinsic pathways of the coagulation system. Inhibition of FXa is expected to exert anticoagulant and antithrombotic effects by decreasing the conversion of prothrombin to active thrombin, thereby diminishing thrombin-mediated activation of the coagulation process, including fibrin formation and platelet activation [1]. DOAC helps to anticoagulate and potentially decrease the risk of systemic thromboembolism.

### **Overall Risk/Benefit Assessment**

Atrial fibrillation (AF) is associated with 5 times increased risk of cerebrovascular events compared to patients in Sinus rhythm [2]. Even in patients undergoing Radiofrequency Ablation (RFA) for atrial fibrillation, the incidence of symptomatic cerebrovascular events (CVE) was 2.3% and 41% of those are from transient ischemic attacks and 25% are from ischemic CVEs, despite being on anticoagulation. The incidence of asymptomatic CVEs rises to 14% after the ablation for AF, detected by Flair enhancement MRI. Multiple trials have shown that the asymptomatic CVEs and/or micro infarcts can increase the odds of having dementia. The incidence of stroke immediately after ablation for left ventricular arrhythmias has ranged from 0 to 2.7% to 7.5% depending on the case series, but there aren't many studies to quantify this problem clearly. Interestingly, the amount of tissue ablated in the ventricles is not any smaller than what is done in the left atrium. Even though the stunning phenomenon that is seen with the left atrial appendage may not be relevant to the ventricular tachycardia ablation, the extensive endothelial denudation and subclinical thrombus formation at the sites of ablation is clearly under appreciated. No active strategies to prevent post ablation systemic thromboembolization are available in patients undergoing left ventricular arrhythmia ablation especially on the left side. Similar to AF, the projected incidence of asymptomatic CVEs may be much higher than the incidence of symptomatic CVEs given the multiple reasons like heat generated from the

ablation, possibility of necrosis of myocardium from ablation and manipulation of the left side of the heart, but currently there are no studies that have focused on the incidence of asymptomatic CVEs. It has been therefore recommended to perform cardioversion or ablation only at therapeutic levels of anticoagulation to decrease the risk of thromboembolism and stroke. So far, there are no trials evaluating the efficacy of unfractionated heparin or newer direct thrombin or factor Xa inhibitors in preventing or reducing symptomatic and also asymptomatic CVEs post-left ventricular arrhythmia ablation. Given the high incidence of symptomatic CVEs and possibility of higher incidence of asymptomatic CVEs which has many prognostic implications, this issue warrants further studies.

Use of oral anticoagulation after left ventricular arrhythmia ablation is not standard of care at this point and is anecdotally used in high risk patients with LV aneurysms and those with severe LV dysfunction. Even when used post ablation anticoagulation with warfarin is fraught with several practical issues including the time to therapeutic range and the need for bridging with unfractionated or low molecular weight heparin with implications to prolonged length of stay and increased bleeding complications. So, the novel non VKA agents probably are a better fit for this specific situation. Early experience with all four currently available agents (Dabigatran, Rivaroxaban , Apixiban and Edoxaban) for periprocedural anticoagulation seems to be safe and efficacious. DOAC is a direct oral inhibitor of Prothrombin/factor Xa inhibitor and thereby mediates its anticoagulation effect . In the recently published double blind randomized clinical trial DOAC was found to be superior to warfarin in decreasing the risk of stroke and also had fewer complications of bleeding and death in patients with atrial fibrillation/flutter .

We believe that peri-procedural DOAC use for left ventricular arrhythmia ablation will provide effective anticoagulation without increasing bleeding complications and may decrease the incidence of both symptomatic and asymptomatic cerebrovascular events, TIAs and strokes.

Magnetic resonance imaging (MRI) is the most commonly used imaging test to detect acute ischemic stroke and asymptomatic CVEs. There is a natural apprehension about the use of MRI scanning in patient with Cardiac Implantable Electrical Devices (CIEDs) . However, there are protocols in place showing MRI examination of patients with CIEDs with minimal or no side

effects . There is increasing data on the safety of the use of MRI in CIED patients which perhaps led to the participating institutions routine use of MRI in defining ventricular scar prior to RF ablation to optimize the treatment strategy and outcomes. The potential for adverse effects on the CIED during MRI of the head is far lower than imaging the chest as the device will not be in the direct MRI field as it is with head scanning. When performed with appropriate monitoring the post left ventricular arrhythmia ablation MRI scanning of the brain can be safe and help us examine an important issue that has not been well defined.

### **Research Hypothesis**

We hypothesize that periprocedural anticoagulation with DOAC (an oral anticoagulation agent with rapid onset of action) for left ventricular arrhythmia ablation decreases symptomatic and asymptomatic cerebrovascular events compared to use of Aspirin only.

### **Study Rationale**

Ventricular tachycardia (VT) is a complex arrhythmia with high mortality rate. ICDs have shown improvement in survival when placed for primary or secondary prevention in such patients, but they are not a cure for VT and they don't prevent recurrences. In addition, painful ICD shocks, not only impair quality of life and psychological health , but they are also associated with increased all-cause mortality. Antiarrhythmic therapy, even though moderately effective, with time and progressive remodeling recurrent VT and subsequent ICD therapies are common. Radiofrequency catheter ablation has emerged as an important therapeutic option to prevent VT recurrences and reduce the frequency of ICD shocks . Catheter ablation provides potential curative treatment in 77-95% of post MI patients presenting with monomorphic VT and around 60% in patients with VT arising from non-ischemic cardiomyopathy . With advancement in technology and newer saline irrigation catheters, the risks are very minimal, with high success rates . In a nationwide sample of 4653 patients who underwent ablation in the United States between 2002 and 2011 for post-myocardial infarction VT, the overall in-hospital complication rate was 11 percent with in-hospital mortality of 1.6 percent . The number of catheter ablations that are being performed for left ventricular arrhythmias continues to grow and varies from region to region and hard to quantify . Both retrograde transaortic approach and trans-septal approach are possible routes for endocardial radiofrequency ablation (RFA) with embolic risk associated with thrombus formation on the ablation catheters and sheaths, micro thrombus

formation at the ablation site during the procedure and after ablation as well. [3]. Over the last decade left ventricular arrhythmia ablation techniques have evolved from being more focal targeted sites to the addition of extensive substrate modification targeting active channels as represented by mid diastolic potentials, late activation potentials etc. in the scar and scar border. This will change the surface area of the ventricular endocardium ablated significantly. The extensive denudation of the ventricular endocardium can obviously become a site of thrombus formation and subsequent embolization. Often times patients with Cardiomyopathy (CM) undergoing left ventricular arrhythmia ablation have poor LV function and have large segments of akinesis/dyskinesis/aneurysms making them more prone for stasis and thrombus formation. Treating them with periprocedural anticoagulation has a potential to significantly decrease the risk of systemic thromboembolization as measured by symptomatic and asymptomatic cerebrovascular events.

#### **STUDY END POINTS:**

##### **Primary Objectives**

Primary end point: To estimate the new symptomatic (Stroke and TIA) and asymptomatic CVEs (brain MRI lesions) and systemic thromboembolism in patients undergoing left ventricular arrhythmia ablation with a novel oral anticoagulant ( DOAC) when compared to aspirin only.

##### **Secondary Objectives:**

- To estimate the impact of DOAC on major peri-procedural bleeding in patients undergoing left ventricular arrhythmia ablation when compared to ASA. Assessment done up to 30 days post procedure.
- To estimate the impact of DOAC on minor peri-procedural bleeding in patients undergoing left ventricular arrhythmia ablation when compared to ASA. Assessments completed at 1 week post procedure and up to 30 days post procedure.

##### **Institutional Review Board/Independent Ethics Committee**

Before initiation of the study, the investigator must have written and dated approval/favorable opinion from the IRB/IEC for the protocol, consent form, subject recruitment materials/process (eg, advertisements), and any other written information should be provided to subjects. The

investigator or sponsor should also provide the IRB/IEC with a copy of the Investigator Brochure or product labeling information to be provided to subjects, and any updates.

The investigator should provide the IRB/IEC with reports, updates, and other information (eg, expedited safety reports, amendments, and administrative letters) according to regulatory requirements or institution procedures.

### **Informed Consent**

Investigators must ensure that subjects or, in those situations where consent cannot be given by subjects, their legally acceptable representative are clearly and fully informed about the purpose, potential risks, and other critical issues regarding clinical studies in which they volunteer to participate.

Investigators must:

- a) Provide a copy of the consent form and written information about the study in the language in which the subject is most proficient prior to clinical study participation. The language must be non-technical and easily understood.
- b) Allow time necessary for subject or subject's legally acceptable representative to inquire about the details of the study.
- c) Obtain an informed consent signed and personally dated by the subject or the subject's legally acceptable representative and by the person who conducted the informed consent discussion.
- d) Obtain the IRB/IEC's written approval/favorable opinion of the written informed consent form and any other information to be provided to the subjects, prior to the beginning of the study, and after any revisions are completed for new information.
- e) If informed consent is initially given by a subject's legally acceptable representative or legal guardian, and the subject subsequently becomes capable of making and communicating their informed consent during the study, then consent must additionally be obtained from the subject.
- f) Revise the informed consent whenever important new information becomes available that is relevant to the subject's consent. The investigator, or a person designated by

the investigator, should fully inform the subject or the subject's legally acceptable representative or legal guardian, of all pertinent aspects of the study and of any new information relevant to the subject's willingness to continue participation in the study. This communication should be documented.

The rights, safety, and well-being of the study subjects are the most important considerations and should prevail over interests of science and society.

## **INVESTIGATIONAL PLAN**

### **Study Design and Duration**

This is a multicenter, randomized, prospective study to determine, if DOAC can be used periprocedural in patients undergoing a scar left ventricular arrhythmia ablation. Patients will be screened from both the clinic setting and upcoming EP lab schedule. The patient's chart will be reviewed and those that meet inclusion/exclusion will be approached for the study. For this study, we intend to enroll 52 consecutive subjects who are undergoing a scar left ventricular arrhythmia ablation at participating institutions if they meet all other inclusion criteria and do not have any exclusion criteria. Patients will be randomized in a 1:1 fashion.

Figure 1 shows the use of ASA or DOAC for left ventricular arrhythmia ablation.

[figure not shown]
Patients undergoing left ventricular arrhythmia ablation will be consented and randomized to either ASA 81 mg or 100 mg daily or DOAC twice daily. Patients randomized to ASA will continue or start ASA 81 mg or 100 mg by mouth daily, and continue up to 30 days after the procedure. Patients randomized to DOAC group will stop the ASA if they are currently taking it; DOAC 5 twice daily will be started 3 hours after hemostasis and continue for 30 days post procedure.

The drugs to which they are assigned to will be continued at least for 30 days post left ventricular arrhythmia ablation. All subjects will be followed from baseline to 30 days post procedure. At this time they will have completed the study and can stop either DOAC and/or Aspirin at the physician's discretion.

*Final revised protocol*

**Figure 1 Therapy initiation protocol for procedures.**

\* In case of any two of the following: age  $\geq$  80 yrs, body weight  $\leq$  60 kg, or serum creatinine  $\geq$  1.5 mg/dL a dose of DOAC at a reduced dose will be initiated.

**Baseline Visit:**

Baseline visit will be conducted within 30 days prior to procedure (unless noted). This visit will include:

- A physical exam and medical history will be performed that includes: height, weight, BMI, NYHC evaluation, blood pressure, pulse, review of systems.
- Labs: Chemistry, CBC, Coagulation, Pregnancy test
- Echo: EF, LA size, Mitral Regurgitation, Aortic Regurgitation, Mitral Stenosis, Aortic Stenosis within 3 months of the procedure
- ECG, MRI, TEE, CT, Device interrogation – most recent within 6 months
- Procedural variables

**Oral Anti-Coagulation/Anti-Platelet Regimen:**

The initiation and stopping of the antiplatelet and DOAC regimens will be based on Figure 1. If subjects are on Aspirin 325 mg, the dose will be changed to 81mg daily. Once vascular access is obtained for ablation, the patient will be started on unfractionated heparin intravenously to maintain the ACT levels  $\geq 300$  msec during the procedure, as deemed appropriate by the operator. Subjects randomized to the DOAC group will be started on oral DOAC at the standard dose of 5 mg twice daily and continued for 30 days post procedure beginning 3 hours after hemostasis. In case of any two of the following: age  $\geq 80$  yrs, body weight  $\leq 60$  kg, or serum creatinine  $\geq 1.5$  mg/dL a dose of DOAC at reduced dose will be initiated for those randomized to the DOAC arm. For drug interactions occurring with DOAC, the concomitant use of the medications per the USPI should be avoided or dose should be adjusted accordingly.

**Ablation Protocol**

A standard left ventricular arrhythmia ablation protocol that is approved at the participating institution and which is in place will be followed. Endocardial ablation, access to the left ventricle is gain via trans-septal approach which is preferred access or via retrograde transaortic approach. When deemed necessary by the operator epicardial access will be obtained and used for mapping and ablation. Left ventricular arrhythmia ablation is performed targeting the clinical VT. A voltage map is created to assess the scar and scar border. If the VT is hemodynamically

stable it will be mapped and ablated using activation and entrainment mapping. If the VT is unstable, pace making, and substrate modification should be done in the target region. The non-clinical VTs are also targeted at the discretion of the operator. Substrate modification including ablation of potential sites of interest with mid diastolic and LAVA potentials should also be targeted. Standard definition for identifying the scar, scar border, pace match, induction protocol and substrate characteristics apply. Programmed stimulation will be repeated after the ablation to look for any inducible Ventricular Tachycardia. Hemodynamic support is used at the discretion of the operator. DOAC will be restarted only after the hemodynamic support has been removed and hemostasis has been achieved.

Hemostasis after procedure is defined as complete absence of any access site bleeding with ACT < 200 seconds and no further need for manual or artificial compression.

#### **Cerebral MRI (as adopted from )**

Study subjects will be screened for new asymptomatic CVEs, within 24 hours after the ablation procedure and again at 1 month post procedure with 1.5 T MRI. A baseline is not done to minimize the number of imaging studies. The Flair sequencing has the ability to delineate a new embolic lesion from an old infarct. This will help reduce the patient exposure to repeated testing. The imaging protocol includes a sagittal T1-weighted spin echo sequence to obtain a better definition of the anterior and posterior cerebral commissures. The parameters of the T1-weighted spin echo sequence were as follows: repetition time/echo time 400/13; slice thickness 5 mm; distant factor 0%; field of view 230 mm; matrix 192×256; and acquisition time 59 seconds. An axial fluid-attenuated inversion recovery (FLAIR) sequence was then used. The parameters of the FLAIR sequence were as follows: repetition time/echo time 8500/112; TI 2500 ms; slice thickness 5 mm; distant factor 30%; field of view 240 mm; matrix 154×256; and acquisition time 3.24 seconds. A diffusion-weighted (DW) sequence, with the use of a single-shot spin echo with echo-planar imaging technique that combined the motion-probing gradient before and after the 180° pulse with echo-planar imaging readout, was obtained; The parameters of the DW sequence were as follows: repetition time/echo time 3200/99; slice thickness 5 mm; distant factor 30%; field of view 230 mm; matrix 128×128; bandwidth 1502 Hz; gradient strength 22 mT; duration of diffusion gradients 31 ms; gradient separation 42 ms in 3 orthogonal directions; and

acquisition time 43 seconds. For each DW sequence, the apparent diffusion coefficient map will be obtained.

On the post ablation MRI, an acute embolic lesion was defined as a focal hyper intense area detected by diffusion weighted sequence (DWI) with or without addition of delayed Fluid-attenuated inversion recovery (FLAIR) positive sequence. The size and localization of the focal lesions will be analyzed certified by radiologist blinded to the clinical status.

Subjects who have the Cardiac electrical implantable devices who are undergoing MRI examination will follow standard protocol which are in place in the institution.

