## STUDY ASSESSMENTS AND PROCEDURES

### Study Schematic

#### Time and Events Schedule

Procedure	Baseline (Within 30 days of the procedure)	Randomization (Within 48 prior to procedure)	Prior to Procedure (Within 24 hours of procedure)	Day of Procedure	24-48 hours Post- Procedure	Discharge	Day 30 (+/- 7 days) Follow- Up
Eligibility Assessments							
Informed Consent	X						
Medical History	X						
Inclusion/Exclusion Criteria	X						
Study Assessments:							
Physical Examination	X			X	X	X	X
Vital Signs	X		X	X	X	X	X
Adverse Events Assessment	X	X	X	X	X	X	X
Evaluation of Bleeding Events	X		X	X	X	X	X
Laboratory Tests	X						
Pregnancy Test	X						
Ablation Procedure				X			
Device Interrogation			X		X	X	X
Cerebral MRI					X		X
Neurology Evaluation NIHSS			X		X		X
EQ5D Survey			X		X		X
Randomization		X					
Dispense Study Drug				X (3 hours post hemostasis)			
Drug Compliance			X	X	X	X	X

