### Day of Procedure

- Physical Exam
- Vital Signs
- Adverse Event Assessment
- Dispense Study Drug
- Evaluation of Bleeding events – including TIMI evaluation
- Ablation Procedure

Post Procedure (within 24-48 hours)

- Physical Exam
- Vital Signs
- Adverse Event Assessment
- Evaluation of Bleeding events – including TIMI evaluation
- Device Interrogation
- Cerebral MRI
- Neurology Evaluation – NIHSS
- EQ5D Survey

Discharge

- Physical Exam
- Vital Signs
- Adverse Event Assessment
- Evaluation of Bleeding events – including TIMI evaluation Device Interrogation

Day 30 Follow up (+/- 7 days)

- Physical Exam
- Vital Signs
- Adverse Event Assessment
- Evaluation of Bleeding events – including TIMI evaluation
- Device Interrogation
- Cerebral MRI
- Neurology Evaluation – NIHSS
- EQ5D Survey

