### Primary End Point Assessment

Incidence of periprocedural embolic events –TIA/CVA/other systemic embolic events immediately after the left ventricular arrhythmia ablation up to 30 days post left ventricular arrhythmia ablation.

The incidence of new asymptomatic cerebrovascular events as documented by MRI at 24-48 hours post procedure and at 30 days after the left ventricular arrhythmia ablation.

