## GLOSSARY OF TERMS

Term	Definition
Adverse Reaction	An adverse event that is considered by either the investigator or the sponsor to be related to the investigational product.
Expedited Safety Report	Rapid notification to investigators of all SAEs that are suspected (related to the investigational product) and unexpected (ie, not previously described in the Investigator Brochure), or that could be associated with the study procedures.
Hemostasis	Defined by no further ooze from groin puncture sites after pressure hold is released. Typically, 3-4 hours post procedure.
SUSAR	Suspected, Unexpected, Serious Adverse Reaction as termed by the European Clinical Trial Directive (2001/20/EC).
Unexpected Adverse Reaction	An adverse reaction, the nature or severity of which is not consistent with the applicable product information (eg, Investigator Brochure for an unapproved investigational product).
Peri-Procedural Bleeding	Occurring prior to the procedure within 48 hours and up to 48 hours post procedure.
Recent MI	Recent is defined as within 30 days of the planned procedure.

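### The first MRI for the silent-lesion part of the primary end point has two windows that meet only at 24 hours, and one of them allows a scan before any DOAC dose

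*Combined protocol and SAP*

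**What the plan says.** **Imaging window.** The Cerebral MRI section sets the first scan as follows: "Study subjects will be screened for new asymptomatic CVEs, within 24 hours after the ablation procedure and again at 1 month". It gives no earliest time. Three other places give a later window:

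- The Primary End Point Assessment: "The incidence of new asymptomatic cerebrovascular events as documented by MRI at 24-48 hours post procedure and at 30 days".
- The visit list under Schedule of Events, which includes the cerebral MRI under "Post Procedure (within 24-48 hours".
- The Time and Events Schedule, which marks the cerebral MRI in the 24-48 hour column.

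**Start of DOAC.** Study Design and Duration says: "DOAC 5 twice daily will be started 3 hours after hemostasis and continue for 30 days post procedure". The regimen section agrees ("continued for 30 days post procedure beginning 3 hours after hemostasis"), and so does the schedule table, which times dispensing on the procedure day as "X (3 hours post hemostasis". The glossary describes hemostasis as "no further ooze from groin puncture sites after pressure hold is released. Typically, 3-4 hours post procedure".

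**No earlier scan.** The Cerebral MRI section states: "A baseline is not done to minimize the number of imaging studies". Any focal hyperintensity on the diffusion-weighted sequence after ablation counts as an acute embolic lesion. The Primary End Point Assessment does not say which scan a day-30 lesion must be new against, and the statistical analysis text plans no summary by time window.

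**The concern.** The silent-lesion count is one component of the primary end point, and this is a multicenter trial. A site that works from the imaging section would scan on the day of the procedure or the next morning. A site that works from the visit list would scan on the next day or the one after. Both would be following the protocol, yet they would measure the same component after different lengths of DOAC treatment, and in some patients after none. The pilot is meant to show whether there is a signal that justifies a larger trial. If scan and dose times are not recorded, nobody can later tell how much drug exposure lay behind a given first scan.

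**Working it through.** The plan gives no figure of its own for exposure at the first scan, so there is nothing to reproduce. The check is addition on the stated times.

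**Inputs**

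- Hemostasis: 3-4 h post procedure (Glossary, given as typical).
- First DOAC dose: 3 h after hemostasis (Study Design and Duration; regimen section; Time and Events Schedule).
- Dosing: twice daily, taken here as every 12 h.
- First MRI: 0-24 h (Cerebral MRI section) or 24-48 h (the other three places).
- Assumption: both windows and the hemostasis time are counted from the end of the procedure.

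**First dose.** Time = hemostasis + 3 h, so 3 + 3 = 6 h to 4 + 3 = 7 h.

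**Time since first dose at the scan.** Scan time minus first-dose time, with a floor of zero:

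| Window | Earliest scan | Latest scan | Time since first dose | Doses taken |
|---|---|---|---|---|
| 0-24 h | before 6-7 h: none | 24 - 7 = 17 h to 24 - 6 = 18 h | 0-18 h | 0-2 |
| 24-48 h | 24 - 7 = 17 h | 48 - 6 = 42 h | 17-42 h | 2-4 |

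Doses fall at 6, 18, 30 and 42 h, or at 7, 19, 31 and 43 h. Either way there are two by 24 h and four by 48 h.

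By the clock, the stretch before the first dose is 6/24 = 25% to 7/24 = 29% of the 24-hour window. This is a share of permitted scan times. It is not a share of lesions, because embolic risk need not be even over time.

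**How firm is 6-7 h?** The Ablation Protocol section defines hemostasis by an ACT limit and the end of compression, without a time, and it holds DOAC until hemodynamic support is removed. Both can push the first dose later. That section also speaks of restarting DOAC, and the schedule marks a compliance check before the procedure; either might suggest earlier use. Figure 1 is not shown in the available text. Three explicit statements nevertheless agree on a start after hemostasis.

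**What the 24-48 h window does not solve.** The Study Rationale expects thrombus both during and after ablation. With no scan before the first dose, even a scan at 24-48 h shows lesions from before that dose together with later ones. A scan taken before the first dose would show only the former.

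**Can the direction of that effect be fixed?** Only if risk before the first dose is equal in the two arms. Under Study Design and Duration, the DOAC arm stops aspirin while the aspirin arm keeps taking it or begins it. Procedural heparin is common to both arms. A sign check, in which every input is an assumption: the aspirin-arm rate is 40%, three quarters of it arises before the first dose, and DOAC prevents 75% of later events.

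- Equal early risk: DOAC rate = 30 + 0.25 × 10 = 32.5%. Difference = 40 - 32.5 = +7.5 points in favour of DOAC.
- Early risk 1.5 times higher in the DOAC arm: 45 + 2.5 = 47.5%. Difference = 40 - 47.5 = -7.5 points.

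This shows only that the sign is not settled. It does not estimate the size.

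**The case against.** **The inconsistency is narrow.** The end point definition, the events table and the visit list agree, and the imaging section is the outlier, with a heading that says it was adapted from another source. Allocation is 1:1 and stratified by site, so sites that use different windows would not, for that reason alone, favour one arm. All of this stands. It makes the correction easy and rules out a claim that the window conflict confounds the arms. It does not remove the conflict, because the imaging section is where a site would look for imaging instructions.

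**Early emboli belong to the question.** The hypothesis concerns periprocedural anticoagulation, and the clinical emboli are counted from immediately after ablation to day 30. Counting everything under the assigned strategy is the intended comparison. This also stands. Including lesions from before the first dose limits interpretation and is not a design error.

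**A stronger reading is tempting.** A reader might infer that these early lesions simply dilute a DOAC benefit toward no difference, and might attach a loss of power to that. The documents do not support it. They give no share of lesions arising before the first dose, no lesion rate after ventricular ablation and no expected efficacy. The different handling of aspirin also means that early risk need not be equal in the arms. The study is described as a pilot for feasibility and safety, with no stated power to lose.

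**Conclusion.** The window is wrong as written. The two instructions for a primary end point scan overlap at a single time point, and the one in the imaging section permits a scan before any study anticoagulant. At the first scan, time since the first dose could be anything from 0 to 42 hours across sites, against 17-42 hours if all followed the other three places. These figures rest on the glossary's typical hemostasis time and on a dose 3 hours later. Slower hemostasis would lengthen the untreated stretch.

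The presence of early lesions on the first scan is a limitation to state, under either window. Its effect on the comparison has unknown size and possibly unknown direction. It should not be described as pure dilution, nor as a bias toward either arm.

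**What to change.** - Change the Cerebral MRI section to 24-48 hours, to match the Primary End Point Assessment, the Time and Events Schedule and the visit list.
- Keep the full composite from ablation onward, analysed by assigned arm (intention to treat), as the primary result.
- Record clock times of procedure end, hemostasis, first dose and first scan on the CRF.
- Add one pre-specified descriptive table by arm: lesions on the first MRI, and lesions at day 30 that are new compared with the first MRI. This also settles what a day-30 lesion is new against.
- State as a limitation that the first scan includes events from before the first DOAC dose, and that the arms differ in aspirin use over that stretch.

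**Cost.** One line of text, four time fields and one table, with no extra scan, visit or change of drug. Each part of the table will hold few events and should carry no test. The day-30 part needs two readable scans per patient, and enrolment leaves only 52 - 50 = 2 patients in reserve. The table cannot isolate silent lesions from before the first dose. That would take an additional scan before dosing, which is not proposed here.
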